7. DRUG INFORMATION

7.1 Ficlatuzumab

7.1.1 Study Drug Materials

The Aveo Pharmacy Manual should be referenced for drug preparation and administration information.

Ficlatuzumab Concentrate for Injection, 50 mg/mL, is formulated in 10 mM histidine buffer pH 5.8. The formulation also includes 142 mM arginine (for isotonicity) and 0.01% polysorbate-80. The product is sterile filtered and aseptically filled into washed and depyrogenated 4-mL and 20 mL glass vials. An excess fill is provided in the vial to ensure that the label fill of 4.0 mL can be withdrawn. The product is a clear to slightly opalescent, colorless to slightly yellow, solution.

Ficiatuzumab Concentrate for Injection is to be administered by IV infusion as an admixture with normal saline solution. The admixture solution in an IV bag is connected to an infusion set containing a 0.22 μ m low protein-binding in-line filter. The IV bag and the infusion set containing the in-line filter have been shown to be compatible with the admixture. The filtered admixture solution is clear to slightly opalescent.

7.1.2 Ficlatuzumab Study Drug Storage

Ficiatuzumab is to be stored under refrigerated conditions (2° C - 8° C) and in a secure location.

Note: No other use of ficlatuzumab study drug intended for use in this trial is authorized by the

sponsor. The investigator (or designee) will be responsible for the appropriate handling and disposition of residual study drug in partially used vials.

Vial Labels: Ficlatuzumab vial labels will bear the appropriate label text for investigational agents, as required by governing regulatory agencies.

Complete study drug information (including packaging, labeling, storage and disposition) is provided in the Ficlatuzumab Investigator's Brochure (IB).

7.1.3 Study Drug Accountability

The local Investigator will be responsible for the supplied study drug, its administration, and accountability. The investigational product must only be used for this protocol and must be stored and accounted for consistent with regulatory requirements, the Aveo Pharmacy Manual, and this protocol. An accurate record of all study drugs received, dispensed, returned, and destroyed must be maintained.

7.2 Cetuximab

Refer to the package insert for additional information.

Formulation: Cetuximab is an anti-EGFR receptor humanized chimeric monoclonal antibody. Cetuximab is expressed in SP2/0 myeloma cell line, grown in large scale cell culture bioreactors, and purified to a high level purity using several purification steps including protein A chromatography, ion exchange chromatography, low pH treatment, and nanofiltration. Cetuximab is not known to be a vesicant.

Safety Precautions: Appropriate mask, protective clothing, eye protection, gloves and Class II vertical-laminar-airflow safety cabinets are recommended during preparation and handling.

Preparation and Administration: Cetuximab must not be administered as an IV push or bolus. Cetuximab must be administered with the use of a low protein binding 0.22-micrometer in-line filter.

Cetuximab is supplied as a 50-mL, single-use vial containing 100 mg of cetuximab at a concentration of 2 mg/mL in phosphate buffered saline. The solution should be clear and colorless and may contain a small amount of easily visible white amorphous cetuximab particulates. DO NOT SHAKE OR DILUTE.

Cetuximab can be administered via infusion pump or syringe pump.

Infusion Pump:

1. Draw up the volume of a vial using a sterile syringe attached to an appropriate needle (a vented spike or other appropriate transfer device may be used).

- 2. Fill cetuximab into a sterile evacuated container or bag such as glass containers, polyolefin bags (eg, Baxter Intravia), ethylene vinyl acetate bags (eg, Baxter Clintec), DEHP plasticized PVC bags (eg, Abbott Lifecare), or PVC bags.
- 3. Repeat procedure until the calculated volume has been put in to the container. Use a new needle for each vial.
- 4. Administration must be through a low protein binding 0.22-micrometer in-line filter (placed as proximal to the patient as practical).
- 5. Affix the infusion line and prime it with cetuximab before starting the infusion.
- 6. Maximum infusion rate should not exceed 5 mL/min (10 mg/min).
- 7. Use 0.9% saline solution to flush line at the end of infusion.

Syringe Pump:

- 1. Draw up the volume of a vial using a sterile syringe attached to an appropriate needle (a vented spike may be used).
- 2. Place the syringe into the syringe driver of a syringe pump and set the rate.
- 3. Administration must be through a low protein binding 0.22-micrometer in-line filter rated for syringe pump use (placed as proximal to the patient as practical).
- 4. Connect up the infusion line and start the infusion after priming the line with cetuximab.
- 5. Repeat procedure until the calculated volume has been infused.
- 6. Use a new needle and filter for each vial.
- 7. Maximum infusion rate should not exceed 5 mL/min (10 mg/min).
- 8. Use 0.9% saline solution to flush line at the end of infusion.

Cetuximab should be piggybacked to the patient's infusion line.

Following the cetuximab infusion, a one-hour observation period is recommended.

Storage Requirements/Stability

Store vials under refrigeration at 2° C to 8° C (36° F to 46° F). DO NOT FREEZE. Increased particulate formation may occur at temperatures at or below 0°C. This product contains no preservatives. Preparations of cetuximab in infusion containers are chemically and physically stable for up to 12 hours at 2° C to 8° C (36° F to 46° F) and up to 8 hours at

v10, 05/23/2023

controlled room temperature (20° C to 25° C; 68° F to 77° F). Discard any remaining solution in the infusion container after 8 hours at controlled room temperature or after 12 hours at 2° to 8° C. Discard any unused portion of the vial.

Supply

Cetuximab is commercially available in the U.S.

8. STUDY PROCEDURES/EVALUATIONS

Schedule of Assessments. See Appendix C for Study Calendar.

Coronavirus/COVID-19 Considerations

As of March 2020, special considerations were implemented in the conduct of clinical trials during the COVID-19 public health emergency. Investigators must determine if changes are needed prior to IRB approval in order to eliminate apparent immediate hazard as allowed by regulations. The safety of subjects and others is priority, and the integrity of the study/study data must also be considered. Any changes/deviations related to the COVID-19 pandemic must be clearly documented as such and particular attention made to account for any missing data.

Should an in-person visit not be feasible or present immediate hazard to the subject, a phone contact should be performed to assess adverse events, concomitant medications, and ECOG performance status, as applicable for the specific visit. Additionally, the study questionnaires, Tobacco Use Assessment and FACT-H&N, can be done by phone or other method as appropriate.

Other potential changes and specific situations can be discussed with the Sponsor-Investigator as applicable/needed.

8.1 Screening/Pre-treatment evaluations

NOTE: All baseline evaluations should be performed as closely as possible to the beginning of treatment but must be performed within 28 days prior to registration unless otherwise indicated.

Written informed consent (prior to screening procedures)

- History and physical examination, including vital signs, weight, height, and ECOG performance status determination
- Documentation of medications subject is currently taking
- Complete blood count, including platelets, and differential
- Blood chemistry studies:
 - o BUN, creatinine, electrolytes (K⁺, Na⁺, Cl⁻, CO₂), glucose, calcium, magnesium
 - Note: Patients may be supplemented to achieve acceptable electrolyte values
- Liver function tests:
 - Total protein, albumin, total bilirubin, AST (SGOT), ALT (SGPT), and alkaline phosphatase
- Documentation of calculation of corrected calcium for eligibility criterion
- For women of child bearing potential: Urine pregnancy test within 14 days prior to registration to rule out pregnancy. (Note, negative pregnancy test must be confirmed again within 3 days prior to first study treatment.)
- Baseline tumor measurements within 28 days prior to registration.
- For oropharyngeal cases and unknown primary: HPV status (p16) status must be known or established and recorded at baseline (randomization is stratified by HPV status and documentation must be sent with the registration; see Section 4).
- Tobacco history assessment form (See Appendix D) (may be performed at screening or prior to study treatment on day 1; the assessment can be performed by method other than in-person, if needed, and the method used must be documented)
- Quality of life assessment (FACT-H&N Symptom Index) (may be performed at screening or prior to study treatment on day 1; the assessment can be performed by method other than in-person, if needed, and the method used must be documented)
- Research blood samples for correlative studies (may be performed at screening or prior to study treatment on day 1)
- Research biopsy of tumor tissue before first study drug administration (See Section
 9.2 for more information.)
- Confirm archived tumor specimens prior to cetuximab exposure are available for correlative research as outlined in Section 9.1. (Note: This is not an eligibility requirement and subjects can be randomized without this confirmation.)

8.2 Registration & Randomization

Once deemed eligible, subject registration will be emailed to the sponsor. The randomization assignment will be returned to the site via email, typically within the day, or the following day

(including weekends).

8.3 Evaluations during study treatment

8.3.1 Every Two Weeks – Day 1 and Day 15 of each cycle (+/- 3 days)

Note: The following may be performed on the day of or within the 3 days prior to study drug administration. If the subject is deemed not acceptable for drug administration, refer to the visit delay and skipped visit description in Section 5.5. Subjects can return within the +3-day window, in 1 week, or for the next regularly scheduled treatment. If appropriate, the visit can be skipped and treatment can occur on schedule with the next regularly scheduled treatment (i.e., 2 weeks later).

- Physical examination, including vital signs, weight and ECOG performance status
- Adverse Event/Toxicity assessment with attribution
- Update of concomitant medications
- Complete blood count, including platelets and differential
- Blood chemistries:
 - o BUN, creatinine, electrolytes (K⁺, Na⁺, Cl⁻, CO₂), glucose, calcium, magnesium
 - Note: Refer to Table 4B regarding grading, repletion, holding treatment, and/or dose reductions.
- Liver function tests:
 - o total protein, albumin, total bilirubin, AST (SGOT), ALT (SGPT), and alkaline phosphatase
- Study drug administration
 - o For both agents: Recalculate the doses of both ficiatuzumab and cetuximab only if there is a ≥ 10% change in weight. Exception: If, in the opinion of the treating investigator, weight change of ≥ 10% is due to edema, recalculation of the ficiatuzumab dose is not required. This decision must be clearly documented.

8.3.2 Every 8 Weeks (the end of even cycles – "Day 28"/8 weeks, 16 weeks, etc.)

- Quality of life assessment (FACT-H&N) end of cycle 2 and cycle 6 only.
 - The FACT-H&N may be done cycle 3, day 1/cycle 7, day 1 for subjects who remain on treatment.
 - If a subject stops treatment per the cycle 2 or cycle 6 scan, the FACT-H&N scheduled for C2D28 or C6D28 can be done at the End of Treatment visit.

- Tumor measurements according to RECIST 1.1 may be done during the last week of an even cycle, by CT scan or MRI.
 - Tumor measurements must be performed every 8 weeks, +/- 7 days for (at least) the first 12 cycles. (See Section 8.3.3 regarding an optional tumor measurements schedule for subjects on treatment longer than 12 cycles.)
 - The schedule is independent of any treatment delays within the 2 cycles since the prior response assessment. (See Section 5.5.1 regarding missed and/or skipped visits.)
 - The Response Assessment must be completed prior to drug administration at day
 1 of the following cycle.
- Research blood samples for correlative studies (these may be drawn simultaneously
 with the pre-treatment labs for the following cycle).

8.3.3 OPTIONAL: Every 12 Weeks Cycle 13+ ("Day 28" of every 3rd cycle after Cycle 12)

Tumor assessments for this trial are performed per standard of care. This optional transition to an every-12-week assessment is consistent with standard of care. This transition is **optional** and can occur **only if** it is appropriate as assessed on a patient-by-patient basis.

Transition to every-12-week tumor assessment will not affect the every-2-week drug administration treatment plan described in Section 5 of this protocol.

- Subjects who remain on treatment past Cycle 12 (Cycle 13+) can be transitioned from every-8-week (+/- 7 days) tumor assessment to every-12-week (+/- 14 days) tumor assessment.
 - For example, a subject who has stable disease, partial response, or complete response per the Cycle 12, Day 28 scan can have their next scan performed on Cycle 15, Day 28, then Cycle 18, Day 28, Cycle 21, Day 28, and so forth.
 - The tumor assessment will be scheduled for Day 28 of every 3rd cycle (+/- 14 days).
 - The schedule is independent of any treatment delays within the 3 cycles since the prior assessment. (See Section 5.5.1 regarding missed and/or skipped visits.)
 - The Response Assessment must be completed prior to drug administration on day 1 of the following cycle.
- Research blood samples for correlative studies will be drawn (blood may be drawn simultaneously with the pre-treatment labs for the following cycle).

8.4 End-of-treatment (EOT) evaluations

- Patients who discontinue treatment for any reason will have an evaluation with the
 following tests, if possible unless performed within the previous 2 weeks (except as
 noted below) and unless otherwise indicated below. The EOT evaluations should be
 performed as soon as possible but within 30 days after the **off-treatment decision**date.
- Physical examination, including vital signs, weight and ECOG performance status
- Adverse Event/Toxicity assessment with attribution
- Update of concomitant medications
- Complete blood count, including platelets and differential
- Blood chemistries:
 - o BUN, creatinine, electrolytes (K⁺, Na⁺, Cl⁻, CO₂), glucose, calcium, magnesium
- Liver function tests:
 - Total protein, albumin, total bilirubin, AST (SGOT), ALT (SGPT), and alkaline phosphatase
- Research blood for correlative studies
- For subjects that end treatment at C2D28 or C6D28, Quality of life (QoL) assessment (FACT-H&N)
 - Subjects that end treatment after C4D28 but prior to C6D28 due to expiration of the study drug will complete the QoL assessment at the EOT visit
- Tumor measurements according to RECIST 1.1 (unless performed within the previous
 28 days if it is an appropriate standard of care procedure the EOT tumor
 measurement will not be performed only for the research)

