5.1.2 Dose and Schedule

Ficlatuzumab will be administered at the dose of 20 mg/kg IV every 2 weeks (+/- 3 days). Ficlatuzumab will be administered over 30-60 minutes.

Ficialty amab dose must be recalculated if there is a \geq 10% change in weight. Exception: If, in the opinion of the treating investigator, weight change of \geq 10% is due to edema, recalculation of the ficialty amab dose is not required. This decision must be clearly documented.

Protocol-specified dose modifications are permitted. See Table 3 below for dose reduction levels.

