8.5 Post-treatment follow-up

8.5.1 Adverse Event and Concomitant Medication Follow-up

AEs and SAEs will be followed per the details below regardless of the reason the subject ended treatment.

- Subjects will be followed for AEs (including SAEs) and pregnancy for at least 60 days after last dose of study drug(s) or until the initiation of subsequent antineoplastic therapy, whichever is earlier.
- Only new AEs that are considered related to the drug and pregnancy need to be documented during the 60 days.

- Any of related AEs that are SAEs must be reported as an SAE to the sponsor.
- AEs that are determined to be related to the study drug, whether documented during treatment or during follow-up, will be followed until resolution or stabilization.
- New concomitant medications do not need to be documented.

If a subject starts any new antineoplastic therapy, collection and follow up of AEs will stop, including AEs considered related/possibly related to the study drug, but SAEs that are considered related/possibly related may require continued assessment. Contact the Sponsor-Investigator for guidance.

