8.5.3 Progressive disease follow-up

Patients who discontinue treatment with progressive disease, experience progression during non-progressive disease follow up, or are censored for progression, will be followed for survival every 12 weeks (+/- 2 weeks) for 2 years.

AE/SAE assessment will be performed by phone contact or per a standard of care visit at least 60 days after the last dose of study drug, and per the requirements in Section 8.5.1.

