- ⁹ A negative pregnancy test is required in women of child-bearing potential within 14 days prior to registration. Negative pregnancy test must be confirmed again within 3 days prior to first drug administration.
- ¹⁰ Archived tumor tissue, preferably the most recent tissue available, may be substituted if the biopsy is not safe and/or feasible, and/or would present unacceptable clinical risk, and the Sponsor has approved omission of the baseline biopsy. See Section 9.2.
- ¹¹ Archived tissue, preferably primary tumor tissue blocks (or slides, if blocks are not available) from procedures **prior to clinical cetuximab exposure.** This is not an eligibility requirement and subjects can be randomized without this confirmation.
- ¹² For scheduling convenience, tumor measurements may occur on day 1 of the following cycle, so long as the scan is done and results are known **prior** to drug administration.
- ¹³ Tumor measurements must be performed every 8 weeks, +/- 7 days, regardless of any delay that occurs within the prior 2 cycles. Subjects who remain on treatment past Cycle 12 can transition to tumor assessments being performed every 12 weeks, +/- 14 days. Refer to Section 8.3.3.
- ¹⁴ FACT-H&N Symptom Index will be performed at baseline and at the end of cycle 2 and cycle 6 only, or when the subject is censored for progression after C4D28 but before C6D28 (see EOT procedures). For scheduling convenience, FACT-H&N Symptom Index may be completed on day 1 of the following cycle or at the EOT visit.
- ¹⁵ For oropharyngeal & unknown primary, p16 status must be established, if not previously known, before randomization.
- ¹⁶ Subject will be followed for AEs/SAEs for 60 days **after last dose of study drug** or until the initiation of subsequent antineoplastic therapy, whichever is earlier. (Refer to protocol Section 8.5.1 for important and specific details on collection and follow up of AEs.)
- ¹⁷ Subjects who end treatment **due to a reason other than progressive disease** will have an AE assessment at the first follow-up visit. (Refer to protocol Section 8.5.1 for important and specific details on collection and follow up of AEs.)
- ¹⁸ Subjects who end treatment **due to progressive disease** will have an AE assessment at least 60 days after last dose of study drug. (Refer to protocol Section 8.5.1 for important and specific details on collection and follow up of AEs.)

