- ¹⁹ Subjects will be followed for survival for 2 years after disease progression.

¹ The End of Treatment visit should be performed as soon as possible, but preferably within 30 days after the off-treatment decision date. Procedures will be performed if not performed in the previous 14 days, except tumor measurements should only be performed if not performed in the previous 28 days and only if it is an appropriate standard of care procedure.

² Refer to Section 5.5.1 which addresses scheduling when there are missed and/or skipped visits due to treatment delays or other.

³ Procedures indicated with "Z" are not required to be performed for the research, but if they are performed for standard of care, the data will be collected. Patients who initiate a new line of antineoplastic therapy will be censored for progression at that time point; research blood will be drawn and they will be followed per the progressive disease follow-up schedule.

⁴ For both agents: Recalculate the doses of both ficiatuzumab and cetuximab only if there is a ≥ 10% change in weight. Exception: If, in the opinion of the treating investigator, weight change of ≥ 10% is due to edema, recalculation of the ficiatuzumab dose is not required. This decision must be clearly documented. Refer to Section 5.

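### The end-of-treatment AE assessment can be waived on the strength of one done before the last dose, so the time after that dose may go unassessed at that visit

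*Combined protocol and SAP*

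**What the plan says.** **The waiver.** Section 8.4 lists "Adverse Event/Toxicity assessment with attribution" among the EOT items, all of which are omitted if done recently ("unless performed within the previous 2 weeks"). Separate provisions are made for quality of life and tumor measurements, not for AEs. Appendix C footnote 1 restates the rule ("Procedures will be performed if not performed in the previous 14 days") and excepts only tumor measurements.

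**The assessment the waiver can rely on.** Section 8.3.1 schedules AE assessment at the Day 1 and Day 15 visits and says of its list: "The following may be performed on the day of or within the 3 days prior to study drug administration". Dosing is "IV every 2 weeks (+/- 3 days" (section 5.1.2). The Appendix C column for the 8-weekly Day 28 evaluation has no AE entry.

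**Later follow-up.**
- Section 8.5.1: "Subjects will be followed for AEs (including SAEs) and pregnancy for at least 60 days after last dose of study drug(s", or until new antineoplastic therapy if sooner. In that period only new AEs judged drug-related (and pregnancy) have to be documented.
- Stopping without progression: section 8.5.2 makes the first follow-up visit the latest point for the AE assessment, and Appendix C footnote 17 says these patients "will have an AE assessment at the first follow-up visit". Visits are every 8 weeks, plus or minus 2.
- Stopping with progression: section 8.5.3, "AE/SAE assessment will be performed by phone contact or per a standard of care visit at least 60 days after the last dose of study" medication.
- Section 12.2 wants AEs of Grade 3 or worse in the database whatever their attribution. Section 12.3 has every SAE reported within 24 hours of notification, whatever its attribution.

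**The concern.** An EOT AE assessment should close the record for the period since the last dose. A waiver based only on how recent the previous assessment was does not secure that, because the previous one may have been made just before the last infusion. It then says nothing about what followed.

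Toxicity is a secondary objective, to be tabulated with 95% exact confidence intervals (sections 10.4.1 and 10.6). If events after the last dose are missed, or are reconstructed from recall weeks later, those proportions can be understated. The events most exposed are non-serious ones judged unrelated, including Grade 3 or worse, and any non-serious event in a patient who moves quickly to another therapy.

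**Working it through.** The plan states no figure on this point, so there is none to reproduce. The check is date arithmetic followed by a comparison of sections.

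**Inputs**
- Waiver window: 14 days (section 8.4; Appendix C footnote 1).
- Lead of the AE assessment before the dose: L = 0 to 3 days (section 8.3.1).
- Nominal dosing interval: 14 days (section 5.1.2).

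**Formula.** Let the last dose be day 0. The last pre-dose assessment is on day -L and the EOT visit on day t, so the assessment is t + L days old. Counting the window back from the EOT visit, and including day 14, the waiver applies if t + L ≤ 14, that is, t ≤ 14 - L.

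The last two columns take a Day 15 last dose and an EOT visit on Day 28, so t = 28 - 15 = 13.

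| Lead L (days) | Latest t with waiver | Age of assessment on Day 28 | EOT AE assessment on Day 28 |
|---|---|---|---|
| 0 | 14 | 13 | waived |
| 1 | 13 | 14 | waived |
| 2 | 12 | 15 | required |
| 3 | 11 | 16 | required |

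So a pre-dose assessment can stand in for the EOT one up to 11 to 14 days after the last dose. At L = 0 that is the whole nominal dosing interval.

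**What the later sections recover**
1. *Timing.* Without progression, the assessment is due by a visit at 8 ± 2 weeks, i.e. 6 to 10 weeks. With progression, it is at least 60 days after the last dose and may be by phone.
2. *Scope.* Section 8.5.1 needs only new related AEs during the 60 days, a period that starts at the last dose. A non-serious unrelated Grade 3 event in that time is wanted under 12.2 but need not be documented under 8.5.1.
3. *Early end.* Sections 8.5.1 and 8.5.2 stop AE collection when new antineoplastic therapy starts; only related SAEs may need continued assessment. A patient who progresses, has the EOT AE assessment waived and starts new therapy before the next contact has no required AE assessment after the last dose.

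**The case against.** The strongest reply is that EOT is not the last AE check. Sections 8.5.1 to 8.5.3 and Appendix C footnotes 16 to 18 require follow-up whatever the reason for stopping, and SAEs travel separately under 12.3. That stands for related AEs and for SAEs, which is why the point is a narrow one. It does not answer the related-only scope or the stop at new therapy.

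Stronger readings that a reader might infer, and why the documents do not support them:

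- *The earlier assessment always precedes the last dose.* It need not. A patient who attends a scheduled visit, is assessed and is not dosed has been assessed after the last dose. Footnote 12 allows the scan on day 1 of the next cycle before dosing, which makes this an ordinary route.
- *The typical patient falls into the gap.* A scan on Days 22 to 28 is 7 to 13 days after a Day 15 dose, but that dates the scan, not the EOT visit. EOT may come up to 30 days after the decision to stop, and a 3-day lead turns 7 to 13 days into 10 to 16. The frequency cannot be derived.
- *One dosing interval in four (stopping at week 8) or in eight (week 16) is lost.* Those ratios count intervals whose assessment may come later. They assume that every dose was given and the waiver was used.
- *Patients without progression also have a gap at the end of the 60 days.* A first visit at week 6 does not end the duty in 8.5.1, and 8.5.2 sets a deadline rather than a closing contact. The size of any gap depends on when the 8-week clock starts. If it starts at discontinuation 7 to 13 days after the last dose, the earliest visit is day 49 to 55 (42 + 7 to 42 + 13) and the nominal one day 63 to 69 (56 + 7 to 56 + 13), which is past day 60.
- *Patients who stop for toxicity are especially exposed.* Section 5.4.4 follows them for 60 days after the last dose or until the event resolves or stabilizes, before they enter the 8-weekly schedule.

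**Conclusion.** The point holds in a limited form. As written, an AE assessment made before the last infusion can replace the EOT one for visits up to 11 to 14 days after that infusion. Later follow-up closes this for most related AEs and, through a separate route, for SAEs. It does not ensure capture of non-serious unrelated events, and a patient who starts new therapy early may have no required AE assessment after the last dose. For others, capture may depend on recall after 6 to 10 weeks, or 60 days or more.

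The 11-to-14-day range assumes that the window is counted back from the EOT visit. Section 8.4 does not say so; if it runs from the off-treatment decision date, the bound applies to that date and the visit itself may be later. The number of patients affected is unknown. The primary endpoint, sample size, power and error rates are untouched. This is a cheap improvement to the completeness of the toxicity data, not a flaw in the design.

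**What to change.** 1. In section 8.4 and Appendix C footnote 1, exempt the AE assessment from the 2-week/14-day waiver unless the earlier assessment was done after the last dose. State that it covers the time since the last pre-dose assessment, and say from which date the window is counted.
2. Reconcile the related-only documentation rule in 8.5.1 with the any-attribution rule for Grade 3 or worse in 12.2. Without this, an added EOT review falls inside the 60 days and could still omit unrelated severe events.
3. Align the AE contact for patients without progression (8.5.2 and footnote 17) with the 60-day follow-up in 8.5.1.

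The cost is wording plus one short AE review at an existing visit or by phone, a mode that 8.5.3 and the COVID-19 text in section 8 already accept. No new tests are needed.

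Section 5.1 puts the last possible ficlatuzumab dose at March 31, 2021, and this version is dated May 2023. If treatment ended as planned, the wording can no longer change what was collected at EOT. The useful step is then to report, by arm, how many patients had no AE assessment after their last dose, alongside the toxicity tables.
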